7.4.1.4 Dose Modification and Toxicity Management of Infusion-reactions Related to Pembrolizumab

Pembrolizumab may cause severe or life threatening infusion-reactions including severe hypersensitivity or anaphylaxis. Signs and symptoms usually develop during or shortly after drug infusion and generally resolve completely within 24 hours of completion of infusion. Dose modification and toxicity management guidelines on pembrolizumab associated infusion reaction are provided in [Table 7-3](#).

Table 7-3. Pembrolizumab Infusion Reaction Dose Modification and Treatment Guidelines

NCI CTCAE Grade	Treatment	Premedication at Subsequent Dosing
Grade 1 Mild reaction; infusion interruption not indicated; intervention not indicated	
 Increase monitoring of vital signs as medically indicated until the participant is deemed medically stable in the opinion of the investigator. 	None
Grade 2 Requires therapy or infusion interruption but responds promptly to symptomatic treatment (eg, antihistamines, NSAIDs, narcotics, IV fluids); prophylactic medications indicated for ≤ 24 hr.	
 Stop Infusion. Additional appropriate medical therapy may include but is not limited to: 
 IV fluids Antihistamines NSAIDs Acetaminophen Narcotics Increase monitoring of vital signs as medically indicated until the participant is deemed medically stable in the opinion of the investigator. If symptoms resolve within 1 hour of stopping drug infusion, the infusion may be restarted at 50% of the original infusion rate (eg from 100 mL/hr to 50 mL/hr.). Otherwise dosing will be held until symptoms resolve and the participant should be premedicated for the next scheduled dose. 
Participants who develop grade 2 toxicity despite adequate premedication should be permanently discontinued from further study drug treatment
	Participant may be premedicated 1.5 hr (± 30 minutes) prior to infusion of pembrolizumab with: Diphenhydramine 50 mg po (or equivalent dose of antihistamine). Acetaminophen 500-1000 mg orally (or equivalent dose of analgesic).

Table 7-3. Pembrolizumab Infusion Reaction Dose Modification and Treatment Guidelines

NCI CTCAE Grade	Treatment	Premedication at Subsequent Dosing

Grades 3 or 4
 
Grade 3: Prolonged (ie, not rapidly responsive to symptomatic medication and/or brief interruption of infusion); recurrence of symptoms following initial improvement; hospitalization indicated for other clinical sequelae (eg, renal impairment, pulmonary infiltrates)
 
Grade 4: Life-threatening; pressor or ventilator support indicated
	
 • Stop Infusion. • Additional appropriate medical therapy may include but is not limited to: • Epinephrine** • IV fluids • Antihistamines • NSAIDs • Acetaminophen • Narcotics • Oxygen • Pressors • Corticosteroids • Increase monitoring of vital signs as medically indicated until the participant is deemed medically stable in the opinion of the investigator. • Hospitalization may be indicated. 
**In cases of anaphylaxis, epinephrine should be used immediately.
 
Participant is permanently discontinued from further study drug treatment.
	
No subsequent dosing

Page 2 of 2

Appropriate resuscitation equipment should be available at the bedside and a physician readily available during the period of drug administration. For further information, please refer to the Common Terminology Criteria for Adverse Events v5.0 (CTCAE) at <http://ctep.cancer.gov>

7.4.1.5 Other Allowed Dose Interruption for Pembrolizumab

Pembrolizumab may be interrupted for situations other than treatment-related adverse events such as medical/surgical events or logistical reasons not related to study therapy. Subjects should be placed back on study therapy within 3 weeks of the scheduled interruption, unless otherwise discussed with the Sponsor. The reason for interruption should be documented in the subject's study record.

7.4.2 Hepatotoxicity Stopping and Rechallenge Rules

Refer to Section 12.7 for details regarding drug-induced liver injury guidelines, as specified in the Guidance for Industry Drug-Induced Liver Injury: Premarketing Clinical Evaluation, July 2009.

7.5 Preparation/Handling/Storage/Accountability

Guidance and information on preparation, handling, storage, accountability, destruction, or return of the investigational products during the study are provided in the IPIM.

7.6 Treatment Compliance

Administration of talimogene laherparepvec and pembrolizumab will occur at the study site.

7.7 Treatment of Overdose

There is no clinical experience with an overdose of talimogene laherparepvec. In the event of a suspected overdose, the subject should be treated symptomatically and supportive measures instituted as required.

For this study, an overdose of pembrolizumab will be defined as any dose of 1000 mg or ≥ 5 times the indicated dose.

No specific information is available on the treatment of overdose of pembrolizumab. In the event of overdose, the subject should be observed closely for signs of toxicity. Appropriate supportive treatment should be provided if clinically indicated.

7.8 Prior and Concomitant Treatment

7.8.1 Prior Treatment

All therapy administered for treatment of melanoma prior to screening must be captured on the appropriate CRF, regardless of duration of time between prior therapy and screening.

For prior therapies that were being taken for melanoma, collect therapy name, indication, dose, unit, frequency, route, start date, and stop date. In addition, for prior PD-1 inhibitors taken for melanoma, also collect clinical response related information to support eligibility (ie, reason for stopping, first date of disease progression, date of confirmed disease progression, best overall response).

All other prior therapies that were being taken/used from 4 weeks prior to screening through the first dose of investigational product, will be collected. For all other prior therapies, collect therapy name, indication, dose, unit, frequency, route, start date, and stop date.

7.8.2 Concomitant Treatment

Throughout the study, investigators may prescribe any concomitant medications or treatments deemed necessary to provide adequate supportive care except for those listed in Section [7.1.7](#).

Concomitant therapies are to be collected from signing of the informed consent form through 30 (+ 7) days after the last dose of investigational product. Subsequent treatment for melanoma will be recorded from the end of investigational product until the subject ends study.

For concomitant therapies being taken for melanoma, collect therapy name, indication, dose, unit, frequency, route, start date and stop date. For all other concomitant therapies, collect therapy name, indication, dose, unit, frequency, route, start date and stop date.

8. Discontinuation Criteria

Subjects have the right to withdraw from investigational product and/or other protocol-required therapies, protocol procedures, or the study as a whole at any time and for any reason without prejudice to their future medical care by the physician or at the institution.

The sponsor can decide to withdraw a subject(s) from investigational product, device, and/or other protocol-required therapies, protocol procedures, or the study as a whole at any time prior to study completion for the reasons listed in Sections 8.1, 8.2.1, and 8.2.2.

8.1 Discontinuation of Study Treatment

Subjects (or a legally acceptable representative) can decline to continue receiving investigational product and/or other protocol-required therapies or procedures at any time during the study but continue participation in the study. If this occurs, the investigator is to discuss with the subject the appropriate processes for discontinuation from investigational product or other protocol-required therapies and must discuss with the subject the possibilities for continuation of the Schedule of Activities ([Table 2-1](#)) including different options of follow-up (eg, in person, by phone/mail, through family/friends, in correspondence/communication with other treating physicians, from the review of medical records) and collection of data, including endpoints, and adverse events, as applicable and must document this decision in the subject's medical records. Subjects who have discontinued investigational product and/or other protocol-required therapies or procedures should not be automatically removed from the study. Whenever safe and feasible, it is imperative that subjects remain on-study to ensure safety surveillance and/or collection of outcome data. The investigator must document the change to the Schedule of Activities ([Table 2-1](#)) and the level of follow-up that is agreed to by the subject (eg, in person, by telephone/mail, through family/friends, in

correspondence/communication with other physicians, from review of the medical records).

Subjects may be eligible for continued treatment with Amgen investigational product(s) and/or other protocol-required therapies by a separate protocol or as provided for by the local country's regulatory mechanism, based on parameters consistent with [Section 12.3](#).

Reasons for removal from protocol-required investigational product(s) or procedural assessments include any of the following:

- Decision by sponsor
- Lost to follow-up
- Death
- Ineligibility determined
- Protocol deviation
- Non-compliance
- Adverse event
- Subject request
- Disease progression
- Requirement for alternative therapy
- Pregnancy

8.2 Discontinuation From the Study

Full withdrawal of consent for a study means that the subject does not wish to receive further protocol-required therapies or procedures, and the subject does not wish to or is unable to continue further study participation. Subject data up to withdrawal of consent will be included in the analysis of the study, and where permitted, publicly available data can be included after withdrawal of consent. The investigator is to discuss with the subject appropriate procedures for withdrawal from the study and must document the subject's decision to withdraw in the subject's medical records.

If a subject withdraws from the study, he/she may request destruction of any samples taken and not tested, and the investigator must notify Amgen accordingly (see [Section 12.6](#) for further details). Refer to the Schedule of Activities ([Table 2-1](#)) for data to be collected at the time of study discontinuation and follow-up and for any further evaluations that need to be completed.

8.2.1 Reasons for Removal From Washout, Run-in or Invasive Procedures

Not applicable.

8.2.2 Reasons for Removal From Study

Reasons for removal of a subject from the study are:

- Decision by sponsor
- Full withdrawal of consent from study
- Death
- Lost to follow-up

8.3 Lost to Follow-up

A subject will be considered lost to follow-up if he or she repeatedly fails to return for scheduled visits and is unable to be contacted by the study site.

The following actions must be taken if a subject fails to return to the clinic for a required study visit:

- The site must attempt to contact the subject and reschedule the missed visit as soon as possible and counsel the subject on the importance of maintaining the assigned visit schedule and ascertain whether or not the subject wishes to and/or is able to continue in the study.
- In cases in which the subject is deemed lost to follow-up, the investigator or designee must make every effort to regain contact with the subject (where possible, 3 telephone calls and, if necessary, a certified letter to the subject's last known mailing address or local equivalent methods). These contact attempts are to be documented in the subject's medical record.

If the subject continues to be unreachable, he/she will be considered to have withdrawn from the study with a primary reason of lost to follow-up.

- For subjects who are lost to follow-up, the investigator can search publicly available records (where permitted) to ascertain survival status. This ensures that the data set(s) produced as an outcome of the study is/are as comprehensive as possible.

9. Study Assessments and Procedures

Study procedures and their time points are summarized in the Schedule of Activities (Table 2-1).

As protocol waivers or exemptions are not allowed if an enrolled subject is subsequently determined to be ineligible for the study, this must be discussed with the sponsor immediately upon occurrence or awareness to determine if the subject is to continue or discontinue study treatment.

Adherence to the study design requirements, including those specified in the Schedule of Activities ([Table 2-1](#)), is essential and required for study conduct.

9.1 General Study Periods

9.1.1 Screening and Enrollment

Informed consent must be obtained before completing any screening procedure or discontinuation of standard therapy for any disallowed therapy. After the subject has signed the informed consent form, the site will register the subject in the IRT and screen the subject in order to assess eligibility for participation. The screening window is up to 28 days.

All screening evaluations must be completed and reviewed to confirm that potential subjects meet all eligibility criteria. The investigator will maintain a screening log to record details of all subjects screened and to confirm eligibility or record reasons for screening failure, (see [Section 6.4](#)) as applicable.

If a subject has not met all eligibility criteria at the end of the screening period, the subject will be registered as a screen fail. Screen fail subjects may only be re-screened once.

Rescreen subjects must first be registered as screen failures in IRT and subsequently registered as rescreeens. Once the subject is registered as rescreened, a new 28-day screening window will begin. Subjects will retain the same subject identification number assigned at the original screening. If the rescreening period begins more than 30 days after the original signing of the informed consent form, all screening procedures, including informed consent, must be repeated within the screening windows specified in the Schedule of Activities ([Table 2-1](#)).

9.1.2 Treatment Period

Visits will occur per the Schedule of Activities ([Table 2-1](#)). On-study visits may be completed within ± 3 days (**excluding week 0, for which the -3 day window does not apply and all assessments should be completed following enrollment, using the + 3 day window for the first dose as described in [Section 7](#), if required**). The date of the first dose of protocol-required therapies is defined as day 1. All subsequent doses and study visits will be scheduled based on the day 1 date. Study treatment is to be administered after all other procedures are completed, unless otherwise stated during each visit that it is required.

9.1.3 Safety Follow-up

Upon permanent discontinuation from the study treatment for any reason, a safety follow-up visit will be performed approximately 30 (+ 7) days after the end of the last dosing interval of investigational product. If an end of treatment decision occurs > 30 (+ 7) days after the last treatment date, then the Safety follow-up should be performed as soon as possible (eg, within a week of the end of treatment decision).

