2.2 Schedule of Activities

Table 2-1. Schedule of Activities

PROCEDURE	Screening			Treatment Period (Weeks) ^a										Follow-up		Notes	
	≤ 28 days	≤ 14 days	≤ 72 hours	0	3	6	9	12	15	18	21	24	>24 ^b	Safety (30 [+7] days post last dose) ^c	Survival ^d		
GENERAL AND SAFETY ASSESSMENTS																	
Informed consent	X																
Inclusion and exclusion criteria	X																
Demographics	X																
Medical, surgical, and medication history	X																
Substance use history	X															Substances: alcohol and tobacco	
Prior anticancer therapy	X																
Physical examination including body weight	X			X										X			
12-lead ECG	X													X			
Vital signs	X			X	X	X	X	X	X	X	X	X	X	Q3W	X		Systolic/diastolic blood pressure, heart rate, respiration rate, and temperature. When scheduled on dosing days, vital signs are to be performed prior to study treatment administration.
ECOG PS	X			X	X	X	X	X	X	X	X	X	Q3W	X			
Adverse events				X	_____										X	X	All adverse events that occur after the first dose of investigational product/study treatment protocol required therapies through the safety follow-up visit will be recorded in the CRF. In addition, talimogene laherparepvec related adverse events that occur after the safety follow-up visit until the end of the long term follow-up will be recorded in the CRF.

Footnotes defined on last page of this table

Product: Talimogene Laherparepvec (T-VEC)

Protocol Number: 20180115

Date: 09 June 2021

Table 2-1. Schedule of Activities

PROCEDURE	Screening			Treatment Period (Weeks) ^a											Follow-up		Notes
	≤ 28 days	≤ 14 days	≤ 72 hours	0	3	6	9	12	15	18	21	24	>24 ^b	Safety (30 [+7] days post last dose) ^c	Survival ^d		

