7.4.1.2 Non-Amgen Investigational Product: Pembrolizumab

The reason for dose change of pembrolizumab is to be recorded on each subject's CRF.

7.4.1.3 Pembrolizumab Dose Modification and Toxicity Management for Immune-related Adverse Events Associated With Pembrolizumab

Adverse events associated with pembrolizumab exposure may represent an immune-related response. These immune-related adverse events may occur shortly after the first dose or several months after the last dose of pembrolizumab treatment and may affect more than 1 body system simultaneously. Therefore, early recognition and initiation of treatment is critical to reduce complications. Based on existing clinical study data, most immune-related adverse events were reversible and could be managed with interruptions of pembrolizumab, administration of corticosteroids and/or other supportive care. For suspected immune-related adverse events, ensure adequate evaluation to confirm etiology or exclude other causes. Additional procedures or tests such as bronchoscopy, endoscopy, skin biopsy may be included as part of the evaluation. Based on the severity of immune-related adverse events, withhold or permanently discontinue pembrolizumab and administer corticosteroids. Dose modification and toxicity management guidelines for immune-related adverse events associated with pembrolizumab are provided in [Table 7-2](#). At the investigator's discretion, talimogene laherparepvec dosing may continue following discontinuation of pembrolizumab.

Table 7-2. Dose Modification and Toxicity Management Guidelines for Immune-related Adverse Events Associated with Pembrolizumab

General instructions:				

 1. The corticosteroid taper should begin when the immune-related adverse event is \leq grade 1 and continue at least 4 weeks. 2. If pembrolizumab has been withheld, pembrolizumab may resume after the immune-related adverse event decreased to \leq grade 1 after corticosteroid taper. 3. Pembrolizumab must be permanently discontinued if the immune-related adverse event does not resolve or the corticosteroid dose is not \leq 10 mg within 12 weeks of the last pembrolizumab treatment. 4. Severe and life-threatening immune-related adverse events should be treated with IV corticosteroids followed by oral steroids. Other immunosuppressive treatment should be initiated if immune-related adverse events are not controlled by corticosteroids. 				

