Examples of such events include invasive or malignant cancers, intensive treatment in an emergency room or at home for allergic bronchospasm, blood dyscrasias or convulsions that do not result in hospitalization, or development of drug dependency or drug abuse.

Recording Adverse Events and Serious Adverse Events

Adverse Event and Serious Adverse Event Recording

- When an adverse event or serious adverse event occurs, it is the responsibility of the investigator to review all documentation (eg, hospital progress notes, laboratory, and diagnostics reports) related to the event.
- The investigator will then record all relevant adverse event/serious adverse event information in the Event case report form (CRF). Additionally, the investigator is required to report a fatal adverse event on the Event CRF.
- The investigator must assign the following adverse event attributes:
 - Adverse event diagnosis or syndrome(s), if known (if not known, signs or symptoms);
 - Dates of onset and resolution (if resolved);
 - **Did the event start prior to first dose of investigational product, other protocol-required therapies;**
 - **Assessment of seriousness;**
 - Severity (or toxicity defined below);
 - Assessment of relatedness to talimogene laherparepvec, pembrolizumab and/or study conduct;
 - Action taken; **and**
 - **Outcome of event**
- If the severity of an adverse event worsens from the date of onset to the date of resolution, record a single event for each increased level of severity on the Events CRF.
- It is not acceptable for the investigator to send photocopies of the subject's medical records to sponsor in lieu of completion of the Events CRF page.

Adverse Event and Serious Adverse Event Recording

- If specifically requested, the investigator may need to provide additional follow-up information, such as discharge summaries, medical records, or extracts from the medical records. In this case, all subject identifiers, with the exception of the subject number, will be blinded on the copies of the medical records before submission to Amgen.
- The investigator will attempt to establish a diagnosis of the event based on signs, symptoms, and/or other clinical information. In such cases, the diagnosis (not the individual signs/symptoms) will be documented as the adverse event/serious adverse event.

Evaluating Adverse Events and Serious Adverse Events

Assessment of Severity

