Duration of response (DOR) is defined as the time from the date of an initial response of CR or PR to the earlier of PD (see definition of BOR per modified RECIST 1.1) or death. Subjects who have not ended their response at the time of analysis will be censored at their last evaluable tumor assessment date before start of the first subsequent anticancer therapy.

- **Durable response rate (iDRR) per modified irRC-RECIST**

iDRR is defined as the percent of subjects with an iCR or iPR per modified irRC-RECIST with an iDOR \geq 6 months. One month will be calculated based on 365.25 days per year.

- **Durable response rate (DRR) per modified RECIST 1.1**

DRR is defined as the percent of subjects with a CR or PR per modified RECIST 1.1 with a DOR \geq 6 months. One month will be calculated based on 365.25 days per year.

- **End of study (trial) date**

The end of study date is defined as the date when the last subject across all sites is assessed or receives an intervention for evaluation in the study (i.e., last subject last visit), following any additional parts in the study (e.g., long-term follow-up), as applicable.

- **Evaluable tumor assessment**

An overall visit response other than unevaluable (UE or iUE).

- **Events of clinical interest pembrolizumab**

Selected non-serious and serious adverse events known as pembrolizumab events of clinical interest (ECI) that occur after the first dose of pembrolizumab through 90 (+7) days after the last dose of pembrolizumab, or 30 (+7) days after initiation of a new anticancer therapy, whichever is earlier must be reported to Amgen within 24 hours.

- **Events of interest (EOI) for talimogene laherparepvec**

EOIs for talimogene laherparepvec are defined in the version-controlled EOI search strategies maintained by Global Regulatory Affairs and Safety (GRAAS) at Amgen for talimogene laherparepvec

[figure not shown]
- **Investigational product (IP)**

[figure not shown]
Investigational product (IP) refers to Amgen IP talimogene laherparepvec and non-Amgen IP pembrolizumab in this study. IP is also referred as study drug or study therapy.

- **Last date known to be alive**

For subjects not known to have died, their last date known to be alive will be determined as the latest date associated with clinic visits before data cutoff date including, for example, but not limited to the following:

1. Survival status: Last subject status date if status of subject is "Alive"

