PFS per modified RECIST 1.1 is defined as the interval from first dose to the earlier event of PD (per modified RECIST 1.1) or death from any cause. Subjects without an event will be censored at their last evaluable post-baseline tumor assessment if available, otherwise will be censored on study day 1.

- **Safety follow-up visit**

Safety follow-up visit will be performed approximately 30 (+7) days after the last dose of IP. If an end of treatment decision occurs > 30 (+7) days after the last treatment date, then safety follow-up will be performed as soon as possible (eg, within a week of end of treatment decision).

- **Serious adverse event (SAE)**

Serious adverse events (SAE) are defined as any adverse event categorized as serious as determined by investigator per protocol defined criteria.

- **Study day**

Study day is calculated from the first day IP is administered (i.e. non-zero dosing).

If visit date is on or after first dose date then:

$$\text{Study day} = \text{visit date} - \text{first dose date} + 1$$

if visit date is before first dose date then:

$$\text{Study day} = \text{visit date} - \text{first dose date}$$

- **Study week 0**

The start of IP administration (i.e. non-zero dosing) to the subject is study week 0. Study day 1 is corresponding to study week 0.

- **Time to subsequent anticancer therapy**

Time to subsequent anticancer therapy is defined as the time from enrollment to the start of subsequent anticancer therapy. Subjects who have not started subsequent anticancer therapy will be censored on their last visit date.

- **Treatment-emergent adverse events (TEAE)**

Treatment-emergent adverse events are defined as any adverse event occurring after initiation of the first dose of study therapy through 30 days after the last administration of study therapy. Adverse events that occur on the same day as the first dose date of study therapy will be treated as treatment-emergent events unless indicated otherwise (for example, if an event occurs on the same date as the first administration of study therapy and the check box indicating prior to the first dose of study therapy is checked on eCRF, then the event will not be counted as a treatment-emergent AE).

[figure not shown]
- **Treatment-emergent serious adverse events (TESAE)**

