Treatment-emergent serious adverse events are defined as any SAE occurring after initiation of the first dose of study therapy through 90 days after the last administration of study therapy or 30 days after the last administration of study therapy if the subject initiates new anti-cancer therapy, whichever is earlier.

SAEs that occur on the same day as the first dose date of study therapy will be treated as treatment-emergent SAEs unless indicated otherwise (for example, if an event occurs on the same date as the first administration of study therapy and the check box indicating prior to the first dose of study therapy is checked on eCRF, then the event will not be counted as a treatment-emergent SAE).

- **Treatment period**

Treatment period is defined as the period between the first date of study therapy administration and 30 days after the last study therapy administration.

6. Analysis Set

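### Non-serious adverse events that start or worsen more than 30 days into a hold of both drugs are treatment-emergent only if dosing resumes, although the protocol records them either way

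*Protocol*

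**What the plan says.** **Counting.** SAP section 5 defines a treatment-emergent adverse event (TEAE) as "any adverse event occurring after initiation of the first dose of study therapy through 30 days after the last administration of study therapy". Investigational product (IP) covers both drugs, and "IP is also referred as study drug or study therapy", so a dose of either one moves the end of the window. The SAP's treatment period ends at the same 30 days. Neither definition mentions holds. Serious events have their own window, "first dose of study therapy through 90 days after the last administration of study therapy or 30 days after the last administration" when new anticancer therapy is started.

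**Collection.** In protocol Table 2-1 and section 9.2.3.1.1.1, adverse events after the first dose "through the safety follow-up visit will be recorded in the CRF". Section 9.1.3 covers late decisions: "If an end of treatment decision occurs > 30 (+ 7) days after the last treatment date, then the Safety follow-up should be performed" soon afterwards, with a week given as the example. SAP section 5 repeats this provision.

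**Holds.** Under Table 7-2, pembrolizumab held for an immune-related event is stopped for good if the event has not resolved, or the steroid dose has not come down, "within 12 weeks of the last pembrolizumab treatment". Section 7.4.1.1 delays talimogene laherparepvec for related immune-mediated events of grade 2 or more, and while steroids for toxicity exceed a set dose. It ends that treatment when certain related toxicities would delay dosing more than 4 weeks past the planned date, or when a related event has delayed it more than 6 weeks.

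**Recording and reporting.** When an event worsens, Appendix 4 (section 12.4) tells sites to "record a single event for each increased level of severity on the Events CRF". SAP section 9.6.1 plans listings of TEAEs, treatment-emergent serious events and deaths on study.

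**The concern.** Two subjects with the same non-serious event on the same day of the same hold are classified differently because of something that happens later. The one who is re-dosed has the event inside the window; the one who never restarts does not. Those who never restart include subjects taken off treatment for toxicity, so the loss is not random with respect to safety.

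TEAE incidence, including grade 3 or higher, is a key secondary endpoint. Other outputs give limited cover. The 90-day window applies only to serious events, and protocol section 9.2.3.1.1.2 leaves it to the investigator whether a grade 4 abnormality is serious. The pembrolizumab events of clinical interest also have a long window, but section 9.2.3.7 limits them to overdose and one pattern of liver tests. An event could therefore be on the case report form and in no planned listing.

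**Working it through.** The documents give no figure for events outside the window, so there is nothing to reproduce. The check is date arithmetic. Day 0 is the last dose of either drug before the hold, and each record is placed by its onset date.

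**Inputs**
- TEAE window: to day 30. Serious-event window: to day 90, or day 30 with new anticancer therapy (SAP section 5).
- Dosing interval: 3 weeks = 21 days (protocol section 7).
- Pembrolizumab limit: 12 weeks = 84 days from the last dose (Table 7-2).
- Talimogene limits: 4 or 6 weeks past the planned dose (section 7.4.1.1).
- Late safety visit: taken as 7 days after the stop decision (section 9.1.3).
- Enrolled: 27 + 15 + 15 + 15 = 72 (SAP section 3.2).

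**Step 1. Classification by onset day.** Re-dosing on day 84 is an illustration; the window then runs to at least day 84 + 30 = 114.

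| Onset day | Treatment ends, non-serious | Treatment ends, serious, no new therapy | Re-dosed on day 84 |
|---|---|---|---|
| 21 | counted | counted | counted |
| 30 | counted | counted | counted |
| 31 | not counted | counted as serious | counted |
| 45 | not counted | counted as serious | counted |
| 60 | not counted | counted as serious | counted |
| 84 | not counted | counted as serious | counted |

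**Step 2. Length of the gap when treatment ends**

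| Limit at which treatment is stopped | Days from last dose | Hold days outside window | Outside window, to late safety visit |
|---|---|---|---|
| Talimogene, 4 weeks | 21 + 28 = 49 | 49 − 30 = 19 | 56 − 30 = 26 |
| Talimogene, 6 weeks | 21 + 42 = 63 | 63 − 30 = 33 | 70 − 30 = 40 |
| Pembrolizumab, 12 weeks | 84 | 84 − 30 = 54 | 91 − 30 = 61 |

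Each row assumes that neither drug is given during the hold and that the final stop decision comes at that limit. If dosing resumes, the gap is 0.

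**Step 3. Maximum grade.** Take an event of grade 2 on day 20 that becomes grade 3, still non-serious, on day 40. It gives two records. If the subject is re-dosed, both fall in the window and the maximum grade is 3. If treatment ends, only the day-20 record does (40 > 30), and the TEAE tables show grade 2. This assumes the second record carries the date of worsening as its onset.

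**Step 4. Weight of one subject.** 1/72 = 1.4 points pooled, 1/27 = 3.7 in cohort 1 and 1/15 = 6.7 in cohorts 2, 3 or 4, if all enrolled subjects are in the Safety Analysis Set.

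**Step 5. Timing of the visit.** Section 9.1.3 counts from the end of the last dosing interval: 21 + 30 = 51 to 21 + 37 = 58 days after the last dose. Table 2-1 (footnote c) and SAP section 5 count from the last dose: 30 to 37 days. The end of collection therefore differs between passages even without a late decision.

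**The case against.** A reader might infer that the toxicity which ends treatment is itself under-counted. The documents do not support that. With dosing every 3 weeks, the toxicity behind a hold will usually have started by about day 21 to 24, when the next dose is due. That is inside the 30 days, so it counts whether or not dosing resumes. The subject is then already in the any-TEAE row, which does not move.

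Several other limits on the point also stand:
- Both drugs must be off. Either may continue after the other is stopped (sections 7.4.1.1 and 7.4.1.3), and any dose keeps the window open.
- The 54-day gap is the longest case and rests on the pembrolizumab limit alone. It does not combine freely with the grade example: for pneumonitis, liver-test elevation, nephritis and neurological toxicity, Table 7-2 ends pembrolizumab at grade 3, so that decision would come at the worsening and not at week 12.
- Days outside the window are not events missed.
- SAP section 9.6.1 does not clearly confine the withdrawal and treatment-related tables to TEAEs, so loss from those is possible but not established.

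Finally, a fixed period after last exposure is a coherent convention, and a window ending at the safety visit would vary with the date of the stop decision, which also depends on outcome. That is a real cost of the first remedy below. It does not remove the present dependence on re-dosing or the absence of a listing.

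**Conclusion.** The point holds in a narrow form. The TEAE window is shorter than the period over which the protocol collects adverse events, and after day 30 of a hold of both drugs the status of a non-serious event turns on whether the subject is later re-dosed. What may be understated is late-onset non-serious events and maximum grade, including non-serious events of grade 3 or higher.

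The gap is about 19, 33 or 54 days of hold, under the assumptions in the working. How many subjects have such holds, and how many events fall in them, cannot be derived from the documents. Each affected subject changes an incidence by 1.4, 3.7 or 6.7 points (pooled, cohort 1, cohorts 2 to 4), and only in a category where that subject has no other qualifying event. This is an inexpensive improvement to the safety reporting; nothing here shows that the safety results as a whole would be misleading.

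**What to change.** Choose one of these in the SAP:

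1. **Extend the window (section 5).** End the TEAE window, and the treatment period, at the later of 30 days after the last administration and the date of the safety follow-up visit, with the extension beyond day 30 stopping at the start of any new anticancer therapy.
2. **Keep 30 days and supplement it (section 9.6.1).** Add a supportive incidence table by maximum grade, and a listing, of all adverse events collected through the safety follow-up visit.

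Under either option, section 5 should say explicitly how events that start or worsen during a hold are classified. The timing of the safety visit must also be reconciled between protocol section 9.1.3 and Table 2-1 with SAP section 5, since option 1 would inherit that conflict.

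The cost is SAP wording plus one derivation, or one table and one listing. Appendix 4 of the protocol leaves the TEAE definition to the SAP, and no new data are needed. Option 1 slightly raises reported incidence and gives a window whose length varies with the stop decision. Option 2 avoids both in the main tables.
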